## C. Significance

**Importance and barriers.** Asthma currently affects more than 6 million children less than 18 years in the United States (8.3% prevalence) and the majority of these children have poor symptom control. In 2016, more than 3.2 million children with asthma experienced an exacerbation necessitating unscheduled care. Exacerbations consist of narrowing of the airway lumen, inflammation, and mucus plugging that can be deadly. Even in non-fatal cases, exacerbations may lead to progressive loss of lung function. To date, the specific factors (and associated symptom profiles) that contribute to asthma exacerbations in children are unclear. Major barriers in the pediatric asthma field include inadequacies of animal models in recapitulating human asthma, a paucity of basic/translational studies, developmental differences that prohibit extrapolation of data from adults to children, and few studies of long-term outcomes in affected children.

**Knowledge gap.** In June 2015, the NINR/Office of Rare Disease Research/NCATS held a workshop on “Advancing Symptom Science Through Symptom Cluster Research.” While the majority of evidence presented at this workshop originated from oncology patients, it was recognized that symptom clusters also occur in other chronic conditions such as asthma and result in decrements in functional status and quality of life. Studies of symptom clusters (and ultimately development of personalized strategies for symptom management) could advance care. However, this area of research is only emerging; existing studies tend to be cross-sectional in nature, ignoring the temporal component of disease progression. To date, there has also been no attempt to identify and phenotype symptom clusters in asthma. Limited symptom science in asthma is a major shortcoming given the chronicity and burden of the disorder that this study is designed to address.

[figure not shown]
## D. Innovation

**Novel concepts.** Whereas other studies have focused on single symptom manifestations (i.e., wheeze or anxiety) in children with exacerbation-prone asthma, this would be the first study to:

- Identify and phenotype **symptom clusters** in children with exacerbation-prone asthma using validated, age-appropriate PROMIS measures and a novel statistical analytical technique in symptom science research, latent transition analysis, to address temporal symptom trajectories,
- Examine whether identified symptom clusters predict objective and patient-reported clinical outcomes (corticosteroid treatment responsiveness and quality of life) that are important to both physicians and affected patients, and
- Link symptom clusters with inflammatory/metabolic pathways that could be targeted with future interventions.

The results of this study could have a significant impact on the assessment and management of children with asthma through identification of high-risk children who might benefit from personalized medicine approaches. While national asthma treatment guidelines do recognize the importance of respiratory symptoms, these guidelines provide no guidance regarding the assessment and management of non-respiratory symptoms in affected children.

To address these critical knowledge gaps, we will perform extensive clinical characterization and state-of-the-art laboratory analyses of children with exacerbation-prone asthma. We will also use an adaptation of the conceptual framework proposed by Brant et al.

that incorporates temporality (**Figure 2**). Our framework proposes that: 1) children with exacerbation-prone asthma and a unique mixture of covariates possess an equally unique set of inflammatory/metabolic pathways that are each associated with symptoms, 2) those symptoms synergize positively or negatively in a symptom cluster that may or may not evolve over time, and 3) symptom clusters impact asthma outcomes.

**Application of novel technology.** The technology and the statistical techniques that we will utilize for this study are cutting-edge. We can multiplex up to 100 biomolecules with magnetic bead technology in 35 microliters of plasma. With only 2.5 microliters of plasma (from a starting volume of only 40 microliters), we can perform chemical partitioning with hydrophilic interaction liquid chromatography (using a novel Merck SeQuant ZIC-HILIC column that is well-known for high-performance selectivity, reproducibility and robustness) for hundreds of small molecules including amino acids and metabolites. This may lead to identification of new biomarkers and opportunities for technology transfer. Our core laboratory facilities are also state-of-the-art (see letters of support). Ultimately, the analyses performed will capitalize upon a rich sample of highly characterized children with exacerbation prone-asthma. Thus we will have the rare opportunity to link symptom clusters with inflammatory and metabolic pathways and key outcomes of clinical relevance to both physicians and patients.

## E. Study population

We will enroll a cohort of 173 children age 6 up to 21 years with exacerbation-prone asthma. Participants will be given the option to either: 1) complete a single study visit, with telephone/email contacts and a review of their electronic medical record for up to 48 weeks after enrollment, or 2) complete the 48-week cohort study with scheduled study visits. Participants who select option 2 with follow-up over 48 weeks will also have the option to complete visits 3, 4 and 5 by telephone.

**Eligibility criteria include the following:**

- Age 6 to less than 18 years at the enrollment visit
- Physician diagnosis of asthma, and
- History of an asthma exacerbation in the previous 12 months, defined as either:
  - Treatment with systemic corticosteroids,\* or
  - Increase in rescue medication use (i.e., abuterol or inhaled corticosteroid) for 24 hours or more, or
  - One or more missed school days due to asthma symptoms, or
  - An unscheduled visit for asthma at either a physician's office, urgent care, hospital emergency room, or
  - Hospitalization for asthma.

*\*In the event of a recent exacerbation treated with systemic corticosteroids or requiring hospitalization, the first study visit will be postponed until two weeks after the last dose of systemic corticosteroids (i.e., prednisone or prednisolone).*

These criteria should ensure a study population with sufficient disease burden, since several prior studies in children have identified these risk factors as significant predictors of poor asthma control and poor future outcomes. Indeed, several prior studies in children have identified a recent exacerbation as the strongest risk factor for subsequent exacerbations regardless of disease severity or use of controller medications. In the third iteration of the NHLBI Severe Asthma Research Program (**SARP**, [name] co-investigator), exacerbations occurred in 39.7% of enrolled children by one year (unpublished data), similar to reports in other cohorts. In SARP, an exacerbation in the previous year was also associated with an 8.94-fold increase in the odds of future exacerbation by one year (95% CI: 4.37, 18.69). Poor asthma symptom control at baseline was similarly associated with increased odds of future exacerbation (OR 2.65, 95% CI: 1.44, 4.82), but there was no additive effect with prior exacerbation. Therefore, we have elected to enroll participants irrespective of asthma symptom control. This will not only facilitate enrollment of participants, but will also promote symptom heterogeneity (which is essential for symptom clustering) and the likelihood of biomarker detection (since inflammation will also be heterogeneous).

**Exclusion criteria for Option 1, a single study visit with telephone/email and electronic medical record follow-up for up to 48 weeks, include:**

- Pregnancy,
- Current smoking,
- Congenital disorders or deformities of the chest wall, lungs or airways,
- History of premature birth <35 weeks gestation, or
- No medical care provider for asthma.

**Exclusion criteria for Option 2, a 48-week cohort study with scheduled study visits, include:**

- Previous allergic reaction to systemic corticosteroids,
- Hepatic, biliary, or renal disease that can interfere with drug metabolism/excretion,

- Chronic medical disorders that may increase the risk of drug-related injury, including osteogenesis imperfecta (increased risk of fracture with corticosteroids), or Crohn's disease, ulcerative colitis, juvenile rheumatoid arthritis, clotting disorders, or Factor deficiency (increased risk of bleeding with corticosteroid therapy),
- Pregnancy,
- Current smoking,
- Congenital disorders or deformities of the chest wall, lungs or airways,
- History of premature birth <35 weeks gestation,
- Unwillingness to receive triamcinolone,
- No medical care provider for asthma, or
- Planning to relocate before study visit 2.

#### **F. Rationale for heterogeneous study population**

In children, asthma symptoms are complex and result from a variety of triggers including allergens, irritants, pollutants, microbes, viruses, psychological stressors and emotions. These triggers induce airway changes such as mucus production, hyperresponsiveness, smooth muscle hypertrophy and constriction that result in respiratory symptoms (and consequent physical, mental and social health symptoms). However, triggers act through different pathways (**Figure 3**) and likely yield different symptom clusters. For example, allergen sensitization is associated with Type-2 (i.e., Th2) eosinophilic inflammation and is thought to be a pivotal risk factor for persistent and severe wheezing and airflow obstruction. By contrast, children with non-Type-2 neutrophilic inflammation tend to wheeze only with respiratory viruses and often have cessation of asthma symptoms during later childhood. Children with non-Type-2 inflammation also have increased IL-8 expression during the course of the exacerbation, which may reflect innate immune impairment in response to viral or bacterial exposures.

[figure not shown]
Nonetheless, the paradigm of “Type-2” versus “non-Type-2” inflammation is not quite as simplistic as depicted and there can be synergy of triggers and pathways. For example, in addition to being a pivotal risk factor for asthma persistence, Type-2 inflammation has also been associated with increased severity of upper and lower respiratory tract infections and a

greater risk of hospitalization for human rhinovirus infection Psychological

stress can also skew T cells toward a Th2 phenotype, since norepinephrine suppresses Th1 cytokines (i.e., IFN- $\gamma$ ) via binding to adrenergic receptors. Additionally, stress promotes DNA methylation and alters expression of numerous genes that regulate behavioral, autonomic, neuroendocrine, and immunological responses. Chronic stress further exerts direct effects on airway smooth muscle through downregulation of the  $\beta$ 2-adrenergic receptor, possibly through dysfunction of the pituitary adenylate cyclase-activating polypeptide 1 pathway which has been previously implicated in children with anxiety and asthma. **We therefore anticipate that the synergy of physical respiratory symptoms with mental and social health symptoms augments inflammation and results in poorer asthma outcomes** compared to children with respiratory symptoms alone. Identification of symptom clusters and their biological features may ultimately advance knowledge of inflammation (and treatment) in children with exacerbation-prone asthma.

## G. Rationale for inflammatory measures

In clinical practice, many children with asthma have ongoing airway inflammation and poor symptom control despite best therapy attempts with controller medications such as inhaled corticosteroids. Inflammation is driven by white blood cell release of cytokines and chemokines, which in turn, promote generation of reactive oxygen species (**ROS**) and free radicals that regulate inflammation through complex interactions with cysteine residues on the surface of proteins. These protein modifications may or may not be reversible and could result in sustained inflammation and tissue damage. For example, nitration and chlorination of catalase results in impairment of the enzymatic catalyzation and breakdown of hydrogen peroxide, whereas nitration of manganese superoxide dismutase and glutathione-S-transferase inhibits

**Figure 3.** Asthma triggers (yellow) and pathways contributing to symptoms/symptom clustering.

detoxification of superoxide and other electrophilic substances. Another example involves glutathionylation of the p50 subunit of the transcription factor, nuclear factor kappa B, which is associated with repressed DNA binding activity.

There is also a wide body of literature demonstrating the inhibitory effects of ROS on corticosteroid responsiveness, through direct actions on the glucocorticoid receptor (**GR**), resulting in a sustained pro-inflammatory state. Ligand binding of the GR in the cytoplasm results in translocation of the activated GR complex into the nucleus, where it binds to the DNA glucocorticoid response element and regulates gene transcription through recruitment of histone deacetylase (**HDAC**) complexes. Whereas increased histone acetyltransferase activity promotes acetylation of histones and inflammatory gene transcription, removal of acetyl groups by HDACs results in gene silencing. Like any protein, the GR contains several cysteine residues that maintain its structure and function; these are also highly sensitive to ROS and can form disulfide bonds that inhibit ligand binding to the receptor or cause the GR to assume a folded conformation, inhibiting nuclear translocation and DNA binding. These actions might account for prior observations of GR dysfunction (with unattenuated proinflammatory cytokine release and increased levels of glucocorticoid hormones) in patients with severe asthma and also in patients with chronic stress and anxiety, depression, and fatigue. **We anticipate that inflammation will be greatest in the cluster of children with the poorest physical, mental, and social health symptoms; we also anticipate that this inflammation (from symptom synergy) will be less responsive to systemic corticosteroid treatment, resulting in persistently poor quality of life.**

#### **H. Rationale for triamcinolone acetonide injection**

At the completion of the baseline visit, a subset participants who consented to the 48 week cohort study will receive intramuscular triamcinolone acetonide (Kenalog,® 1 mg/kg, up to 40 mg maximum) administered deep in the gluteal muscle by a trained registered nurse. Corticosteroids are the cornerstone of treatment for asthma; intramuscular triamcinolone was selected as the treatment of choice over oral prednisolone or inhaled corticosteroids to allow for characterization of corticosteroid insensitivity without the confounding effects of poor adherence or inadequate drug delivery or absorption. We further considered the pharmacology of corticosteroids. Because triamcinolone has 20% more glucocorticoid activity than prednisolone, triamcinolone 1 mg/kg will ensure that participating children have a sufficient dose of corticosteroid to achieve the desired potential anti-inflammatory effects. In previous studies of adults, a single dose of 80 mg of triamcinolone significantly improved lung function and asthma symptoms in the majority of patients. Given several previous studies in children and our own published studies of triamcinolone responsiveness in children with asthma, a dose of 1 mg/kg of triamcinolone should elicit a clinical response. Because inclusion is limited to children with a recent exacerbation (many of whom will have poor symptom control and all of whom are at risk for future exacerbation), all participants have the potential to benefit from this procedure. The safety of our dosing strategy has also been well established. In our previous study ([name] R01NR012021), the triamcinolone injection was well tolerated and no unexpected adverse events were reported. Expected adverse events

within 24 to 48 hours of triamcinolone receipt included tenderness (25%), warmth (3%), and mild itching (2%) at the injection site. No activity limitation from injection pain was reported and there were no reports of subcutaneous atrophy following the injection. Other unrelated adverse events included dizziness (n = 1), atopic dermatitis (n = 1), facial rash (n = 1), headache (n = 1), nausea and vomiting (n = 1), pharyngitis (n = 1), and cough (n = 1). The distribution of adverse events did not differ according to asthma severity or treatment response group, and each event resolved within 14 days. In the proposed study, the one-time administration of 1 mg/kg of triamcinolone (40 mg maximum) has documented safety and will result in a significantly smaller cumulative corticosteroid dose than that used by other pediatric investigators.

## I. Overview of study design

We will enroll a cohort of 173 children age 6 up to 21 years with exacerbation-prone asthma. Participants will be given the option to either: 1) complete a single study visit, with telephone/email contacts and a review of their electronic medical record for up to 48 weeks after enrollment, or 2) complete the 48-week cohort study with scheduled study visits (**Appendix 1**). Participants who select option 2 with follow-up over 48 weeks will also have the option to complete visits 3, 4 and 5 by telephone.

### **Option 1: A single study visit with telephone/email and electronic medical record follow-up for up to 48 weeks**

Visit 1 (enrollment) will involve informed consent and participant characterization for the purpose of symptom cluster identification. After this visit is completed, the participant's medical record will be reviewed for up to 48 weeks to assess for asthma exacerbations requiring medical treatment. Telephone/email contacts will also be attempted at 24 weeks and 48 weeks after this visit to ensure that asthma exacerbations treated outside of a healthcare facility or other asthma exacerbations that are managed at home are accounted for.

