### **Option 2: A 48-week cohort study with scheduled study visits**

Visit 1 (enrollment) will involve informed consent and participant characterization for the purpose of symptom cluster identification and receipt of systemic triamcinolone acetonide. Visit 2 will involve assessment of triamcinolone responsiveness. Visits 3, 4 and 5 are follow-up visits to assess the temporal stability of the symptom clusters. Visits 3, 4 and 5 can be completed in person or over the telephone.

This research is considered a clinical trial, because it involves an intervention (triamcinolone injection), and the study is designed to evaluate the efficacy of the intervention on symptoms and quality of life. The Emory Office of Clinical Research will facilitate the registration, periodic updates, and results reporting within ClinicalTrials.gov for the duration of the study.

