## J. Outcome measures

Asthma exacerbations are an outcome of interest for all participants.

For participants enrolled in the 48-week cohort study, the primary outcome is corticosteroid treatment responsiveness, assessed 14 days after systemic triamcinolone administration (at visit 2). Responsiveness will be determined from the mean difference in the Asthma Control Questionnaire (**ACQ**) score between visit 1 (baseline) and visit 2 (14 days), with a reduction of 0.5 considered a minimally important difference.

The secondary outcome for participants enrolled in the 48-week cohort study is quality of life, assessed by the PROMIS Pediatric Asthma Impact Scale (**PAIS**) at visits 3, 4 and 5. As with all PROMIS measures, the PAIS is scored on the T-score metric, with higher scores reflecting more of the concept being measured. On the T-score metric, 50 is the mean of the reference population and 10 is the standard deviation; thus scores of 40 and 60 are one standard deviation lower and higher than the mean of the reference population, respectively.

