**Follow-up visits (Visits 3 and 4), Study Week 16, 32 (window +4 weeks)**

1. Brief physical examination (by RN) including height and weight performed\*
2. Medical history obtained
3. Urine pregnancy testing\*
4. Asthma control evaluation (Asthma Control Questionnaire and Asthma Control Test)
5. Administer PROMIS symptom questionnaires
6. Measure exhaled nitric oxide\*
7. Perform spirometry with oscillometry\*

\*procedure will not be performed if follow-up occurs by telephone

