Retention of research participants is essential for this longitudinal study. In our experience, the best retention method for participants in long-term clinical studies is education and continual "reminders." For all participants enrolled in our clinical research studies, including the study proposed here, newsletters are distributed every 3 months (by mail or email) that include educational material about respiratory health, bulletins of important issues that affect patients (flu vaccines), and study updates. We also have several additional methods to encourage continued involvement in our studies, including distribution of materials with our logos and contact numbers and other continual "reminders" of study involvement (refrigerator magnets, pens, mugs, t-shirts or blankets). Other retention efforts will focus on ease of the majority of visits and informational rewards (such as asthma education). Visits will be at times convenient to the parents, many of whom are employed. Appointments after school will also be available. Study team members will be available to answer questions about asthma. The study physician will also be available by phone during off-hours to aid in the management of adverse events including asthma exacerbations.

Participants will also be paid for their time and participation in the study. While we will enroll 173 children, we expect some dropout to occur. Study visits will be pro-rated accordingly, and families will be paid at the end of each visit. Parking passes are also provided so that families do not have to pay for parking. In the event that transportation is a challenge, we also pay for taxis to pick up participants at their homes and drive them to the study site.

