## **T. Sample size**

The sample size is 173 participants age 6 up to 21 years, which accounts for a conservative attrition rate of 15% (final N=147). The following assumptions were used for sample size calculations:

- Identification of 4 symptom clusters resulting in 3 degrees of freedom,

- >80% desired power for a chi-square test of multiple proportions,
- Two-tailed significance level of 0.05 if the effect size (W) is small-to-medium by Cohen's convention and equivalent to W=0.275 (small effect: W=0.10, corresponding odds ratio=1.49; medium effect: W=0.30, corresponding odds ratio=3.45), and
- Sample size allocation ratio of 1-2 per cluster group and sample sizes of at least 20 per group.

The sample size calculations with the above parameters should achieve at least 80% power as shown in **Table 3**.

For the secondary outcome, The sample size of 173 children necessary for the primary outcome should achieve >85% power to detect a difference of 0.2 between group means (considered a small effect size  $d$ ) with standard deviation of 0.20. Power >80% is achieved if the mean difference between groups and associated standard deviation is slightly larger but still small (0.25-0.30). In our prior study of triamcinolone administration to children with asthma, mean ( $\pm$  standard deviation) quality of life scores (on a different instrument, the Asthma Quality of Life Questionnaire) were 6.17 ( $\pm$  0.75) and 5.07 ( $\pm$  0.99), respectively. If similar differences are noted between two symptom cluster groups, we should have >90% power for the primary outcome and >95% for the secondary outcome if the groups have at least 20 participants. With smaller group sizes of only 13 participants, power would be >81% and >89% for the primary and secondary outcomes, respectively.

Drop-out	df	Power if effect size is:				
		0.250	0.275	0.300	0.325	0.350
10% (N=156)	3	0.749	0.833	0.897	0.941	0.969
	4	0.703	0.795	0.867	0.920	0.956
	5	0.664	0.760	0.840	0.900	0.942
12.5% (N=151)	3	0.734	0.820	0.886	0.933	0.963
	4	0.687	0.780	0.855	0.911	0.949
	5	0.648	0.744	0.826	0.889	0.934
15% (N=147)	3	0.721	0.808	0.877	0.926	0.959
	4	0.674	0.767	0.844	0.903	0.943
	5	0.634	0.731	0.814	0.878	0.927

**Table 3.** Estimated power.

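### Exacerbations are an outcome for every child, but medical-record review to week 48 is written only for Option 1, so treated exacerbations have a contact-independent source in one option only

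*Combined protocol and SAP*

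**What the plan says.** Section J states: "Asthma exacerbations are an outcome of interest for all participants". Section U then lists exacerbation rates among the Aim 4 outcome variables, and the Aim 4 hypothesis in Section B expects more exacerbations in the most socially vulnerable children.

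For Option 1, Section I provides two sources. The child's "medical record will be reviewed for up to 48 weeks to assess for asthma exacerbations requiring medical treatment". In addition, "Telephone/email contacts will also be attempted at 24 weeks and 48 weeks after this visit", so that events treated outside a healthcare facility or managed at home are counted. Sections E and I and the Option 1 headings attach record review to this option by name.

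For Option 2, Section I says only that the child will "complete the 48-week cohort study with scheduled study visits". The purpose given for the later visits is a different one: "Visits 3, 4 and 5 are follow-up visits to assess the temporal stability of the symptom clusters". Section K and Appendix I list no record review for Option 2. The one item that could capture exacerbations is "Medical history obtained", at visits 2 to 5, of which visits 3, 4 and 5 may be done by telephone.

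Section Q anticipates loss: "While we will enroll 173 children, we expect some dropout to occur". Section T puts it at 15%, from 173 to 147.

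**The concern.** One outcome is collected in two ways. In Option 1 a medically treated exacerbation can be found in the chart even if the family never answers a call. In Option 2 the same event is found only if the family completes a later contact and reports it. Once an Option 2 child cannot be reached, nothing in the plan observes exacerbations for the rest of the 48 weeks.

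The outcome at stake is the Aim 4 exacerbation rate, together with any description of exacerbations that pools the options. Families choose their option, and Option 2 carries extra exclusions and the triamcinolone injection, so the way events are found is tied to who the children are. If loss in Option 2 is related to social vulnerability or symptom burden, which is plausible but not stated in the documents, events would go missing unevenly across the groups that Aim 4 compares.

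**Working it through.** **1. The two options side by side**

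| | Option 1 | Option 2 |
|---|---|---|
| Record review to week 48 | Yes | Not listed |
| Post-baseline contacts | Weeks 24, 48 | Weeks 2, 16, 32, 48 |
| Longest scheduled gap between contacts | 24 weeks | 16 weeks, before windows |
| Treated event, family unreachable | Chart can show it | No source |
| Home-managed event | Contact report | Contact report |

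Appendix I has a row for medical history review at every Option 2 visit. This is not the chart review. It is tied to each contact, and for Option 1 the plan lists medical history at the calls separately from record review, so it treats the two as different things.

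**2. The plan's own figures.** 173 × 0.85 = 147.05, which gives the stated final N of 147 and a loss of 26. Power for the 3-df chi-square test at W = 0.275 and N = 147 has noncentrality 147 × 0.275² = 11.12 and comes to 0.808, as in Table 3. Both figures reproduce, but the power concerns the ACQ response. The documents give no sample size or power for exacerbations.

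**3. Follow-up time lost.** Assume that all 173 choose Option 2 and that the 15% applies to them.
- Planned follow-up: 173 × 48 = 8,304 child-weeks.
- All 26 leave after visit 2: 26 × 46 = 1,196, and 1,196 / 8,304 = 14.4%.
- Dropout uniform over 48 weeks, mean loss 24 weeks: 26 × 24 = 624, and 624 / 8,304 = 7.5%.

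**4. Children with an unrecorded exacerbation.** The inputs are 39.7% by one year (Section E, from another cohort) and 53.7% per year (Section A, national figure). Assume a constant hazard λ = −ln(1 − p) / 52 per week, the same for children who are lost and children who stay.
- All leave after visit 2: the probability of an event in the 46 unobserved weeks is 1 − exp(−46λ), which is 0.361 at 39.7% and 0.494 at 53.7%. Times 26, this is 9.4 and 12.8 children.
- Uniform dropout: the mean probability is 1 − (1 − exp(−48λ)) / (48λ), which is 0.201 and 0.284. Times 26, this is 5.2 and 7.4 children.
- If half the cohort chooses Option 2, 13 are lost: about 3 to 4 children with uniform dropout and about 5 to 6 if all leave after visit 2.

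**5. Effect on a proportion.** Suppose the true 48-week proportion is 39.7%, 15% are lost independently of exacerbation, and children who are lost are counted as event-free after their last contact. The observed Option 2 proportion is then:
- 33.7% if all loss comes before any follow-up contact (0.397 × 0.85);
- 36.1% if last contacts are spread equally over weeks 2, 16 and 32;
- 37.0% if loss is uniform over 48 weeks.

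**The case against.** The strongest reply is that Option 2 has the more intensive follow-up. It schedules four post-baseline contacts against two, at shorter intervals, and three of the four may be by telephone. While a family responds, home-managed events, which no chart shows, may be captured better in Option 2. This stands. It means that the direction of the between-option difference cannot be read from the plan. A reader might infer that Option 2 simply under-counts exacerbations; the documents do not support that.

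A reader might also infer that an Option 2 child who stops coming in has no other route, or loses the week-48 Asthma Impact score. That is not so. A telephone visit 5 still collects medical history, ACQ, ACT and the PROMIS forms, and Section L lists Asthma Impact among these. Only children who cannot be reached at all are affected, and a chart review could not recover a questionnaire score for them.

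The stakes are also limited. Exacerbations are neither the primary nor the secondary outcome, and Section U gives no exacerbation analysis for Aims 1 to 3. It describes Aim 4 as exploratory, without multiplicity adjustment, and treats dichotomised exacerbation occurrence as not pre-specified. No comparison of Option 1 with Option 2, or of treated with untreated children, is planned.

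These points narrow the concern but do not answer it. Nothing else in the plan supplies the missing source. The HIPAA waiver in Section Q is for finding eligible children. Reporting hospitalizations as serious adverse events (Section R) requires that the study first learns of them, and many exacerbations under the eligibility definition in Section E are not hospitalizations. The missing-data text in Section U concerns the latent transition analysis.

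**Conclusion.** The point holds in a limited form. As written, medically treated exacerbations have a contact-independent source in Option 1 only, and Option 2 children who become unreachable are unobserved after their last contact. It would go too far to say that these children drop out of the outcome: they contribute up to that contact.

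The size is modest and depends on an Option 2 share that the plan does not give. With all 173 in Option 2, roughly 5 to 7 children would have an unrecorded exacerbation under uniform dropout, and about 9 to 13 at the extreme; half the share gives half the count. These figures rest on 15% attrition applying to Option 2, a constant hazard unrelated to dropout, and frequencies from other populations whose exacerbation definition may differ from this study's. Some of the events would be home-managed, and a chart review would not find those. Bias in the Aim 4 comparison is possible if loss tracks social vulnerability, but the documents do not establish it. No stated sample size or power changes. The repair is worth making because it is cheap and uses a process that the study already runs.

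**What to change.** In Section I (the overview and the Option 2 paragraph, with the matching sentence in Section E), the Option 2 visit lists in Section K, and Appendix I, apply the Option 1 record review to week 48 to every Option 2 participant. Include those who stop visits without withdrawing permission for record access.

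In Sections J and U:
- use one exacerbation outcome definition for both options;
- report record-confirmed treated events and contact-reported home-managed events separately as well as combined;
- base rates on each child's observed follow-up time, so that weeks with no source are not counted as event-free;
- include option as a covariate in any pooled exacerbation analysis.

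The cost is a protocol amendment, record-access wording in the Option 2 consent if it is not already there (the consent text is not part of the document reviewed), and some chart-review time. The review can be done retrospectively where permission allows, so a late change still recovers data. Care received outside the record system would still be missed, but in both options alike.
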